3.4 STUDY CALENDAR

Study	Pre-treatment	Induction Treatment							Extended Treatment				End of Treatment and Follow-Up	Disease Progression at any Time Point ^{l,p}
		Cycle 1					Cycle 2-8		Extended Dosing Phase (Phases I and II)				Every 3-6 months ^(j,p,r,s,t) or annual ^(v)	
		Day 1	Day 2	Day 8	Day 15	Day 22	Day 1 ^p	CR Achieved/End of Cycle 8 ^{m,n,o,p}	Day 1 of Cycles 9, 12, 15, 18, 21, 24, 27, 30 ^{c,e,r,s}	Day 1 Cycles 9, 12, 15, 18 ^{p,r,s}	Day 1 Cycles 9-32 ^{r,s}	Phase I-CR Achieved (Cycle 9-20)/ End of Cycle 20 and Phase II-CR achieved (Cycle 21-32)/ Treatment termination ^{m,n,o,p,r,s}		
Medical Record Review	x												x	
H&P	x	x	x	x	x	x	x		x					
ECOG	x						x		x					
Informed Consent	x													
Routine Labs ^a	x	x	x	x	x	x	x		x				x	x
Urine for UPEP and IFE ^m	x	x ^m					x ^m	x ^m	x ^m			x ^m	x	x
Viral Studies ^b	x													
Register for REMS®	x													
Pregnancy Test ^c	x ^c	x ^d	x ^d	x ^e	x ^e	x ^e	x ^c		x ^{c,e}		x ^{c,e}	x ^c	x ^e	
Myeloma Tests ^f	x						x		x			x ^q	x	x
Pharmacokinetic Studies		x ^k					x			x				
Research Blood/Urine	x		x	x	x		x	x	x			x ^r	x	x
Bone Marrow/Aspirate	x ^g		x ^h					x ^{i,o}				x ^{i,o}	x ⁱ	x
Skeletal Survey	x													
FDG PET-CT	x							x ⁿ				x ⁿ	x ⁿ	x
DW-MRI												x ^u		

the PI. In certain circumstances (at the discretion of the patient and PI), patients who are being followed by an outside oncologist and institution may continue to stay on study without a formal NIH visit, but by investigator-patient or investigator-physician phone or email communication to capture clinical and laboratory data. During the follow up phase, research blood/urine collection is optional and at the discretion of the PI.

- k. Pharmacokinetic studies Cycle 1 Day 1 will be collected at the following time points: pre-dose, end of infusion, 5, 15, and 30 minutes and 1, 1.5, 2, 4, 6, and 24 hours post administration for carfilzomib.
- l. At disease progression, marrow and FDG-PET/CT are optional.
- m. Urine for protein electrophoresis (UPEP) and immunofixation to assess for monoclonal protein in the urine (Bence-Jones proteinuria) at baseline, day 1 of each cycle during cycles 1-8, day 1 of every third cycle during cycles 9-32, and at treatment termination. If patient achieves CR, a 24 hour UPEP will be performed to confirm CR status. In patients whose measurable disease is best determined by measuring Bence-Jones protein quantification, a 24 hour UPEP will be performed at baseline, day 1 of each cycle 1-8, and day 1 of every third cycle during extension phase I and II. Otherwise, 24-hr UPEP Bence-Jones quantification will be estimated from random UPEP specimens performed at baseline, day 1 of each cycle 1-8, and day 1 of every third cycle during extension phase.
- n. FDG-PET scan will be performed on patients in the Molecular Imaging Program at baseline, during cycles 1-8 if patient achieves CR and/or at the end of cycle 8 if no CR is achieved, during cycles 9-20 (extended dosing phase I) if patient achieves CR and/or at the end of cycle 20 if no CR is achieved, and during cycles 21-32 (extended dosing phase II) if CR is achieved or at treatment termination. FDG-PET scan can be performed +/- 21 days of intended cycle day. During extension phase lenalidomide, FDG-PET scans are optional for those patients that are MRD negative at the end of cycle 8 regardless of response. During the follow up phase, PET scans will be done on a yearly basis at the discretion of the PI.
- o. Bone marrow biopsy and aspirate will be performed on patients at baseline, during cycles 1-8 if patient achieves CR or at the end of cycle 8 if no CR is achieved during cycles 9-20 (extended dosing phase I) if patient achieves CR or at the end of cycle 20 if no CR is achieved, and during cycles 21-32 (extended dosing phase II) if CR is not achieved or at treatment termination. Bone marrow aspirate and biopsy can be performed +/- 21 days of intended cycle day. For patients who are on extended dosing with lenalidomide and are found to be negative by immunohistochemistry and flow cytometry of the bone marrow (MRD negative), clearance of abnormal protein in blood and/or urine does not mandate a repeated bone marrow and the results will be interpreted as complete response. However, a bone marrow will be repeated at the discretion of investigator.
- p. Variations of +/- 3-14 days of scheduled visits are permitted. For patients who choose to undergo stem cell harvest, next cycle may be delayed for up to 5 weeks. In the follow up phase, patients may be allowed to "skip" appointment visits at the discretion of the PI.
- q. Repeat myeloma tests at treatment termination.
- r. Within 7 days prior to D1 of each cycle
- s. May be delayed up to 7 days per PI discretion for clinical or logistical reasons
- t. Every attempt should be made to have all subjects complete a safety visit approximately 30 days following the last dose of study therapy. If subjects cannot return to clinic, this may be done by phone.
- u. With amendment P, patients will be offered DW-MRI on an annual basis; these are optional. Diffusion weighted MRI (DW-MRI) will also be performed at the discretion of the PI. DW-MRI will be performed by standard techniques in the NCI Molecular Imaging Branch.

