5 BIOSPECIMEN COLLECTION

5.1 CORRELATIVE SAMPLES FOR RESEARCH/PHARMACOKINETIC STUDIES

NOTE: Effective with Amendment L (version date 07/15/2015), bone marrow aspirate and biopsy will be obtained for research studies at the discretion of the PI. Effective with Amendment N (version date 07/25/2017), samples for next generation sequencing (NGS) were added.

Correlate	Baseline	Day 2 Post 24 Hour Infusion	During Cycles 2-8 If CR achieved or End of Cycle 8	During Extended Dosing Phases (Phase I and II) if CR achieved during cycles 9-20/ End of cycle 20 and if CR achieved during cycles 21- 32/End of Cycle 32/treatment termination	Progression of disease
Pathology/IHC	X		X	X	X
Multiparametric Flow Cytometry	X		X	X	X
FISH/Cytogenetics (optional)	X				X
Molecular pathology for light or heavy chain immunoglobulin rearrangement and/or KRas and NRas mutation analysis	X		X (optional)	X (optional)	X
CD138+ Sorting/GEP Profiling/Microenvironment	X	X	X	X	X
Flow cytometry for proteasomes	X	X	X (optional)	X (optional)	X
Flow cytometry for autophagy	X	X	X	X	X
Other research labs as below including Next Generation Sequencing (NGS)	(Added with Amendment N; subjects beyond this cycle)			X	X
Storage	X	X	X	X	X

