6.3.3.1 Evaluation of Response Criteria

- **Stringent Complete Response (sCR)**

Complete Response as defined below plus:

Normal FLC ratio and absence of clonal cells in bone marrow by immunohistochemistry or immunofluorescence (presence/ absence of clonal cells is based on the kappa/ lambda ratio.

- **Complete Response (CR)**

Negative immunofixation on the serum and urine and disappearance of any soft tissue plasmacytomas and $\leq 5\%$ plasma cells in bone marrow

- **Near Complete Response (nCR)**

Defined as absence of myeloma protein on electrophoresis, independent of immunofixation status[\(6, 21\)](#)

- **Very Good Partial Response (VGPR)**

Serum and urine M-protein detectable by immunofixation but not on electrophoresis or 90% or greater reduction in serum M-protein plus urine M-protein level < 100 mg per 24h. If the serum and urine M-protein are unmeasurable, a $\geq 90\%$ decrease in the difference between involved and uninvolved FLC levels is required in place of the M-protein criteria.

- **Partial Response (PR)**

$\geq 50\%$ reduction of serum M-protein and reduction in 24-h urinary M-protein by $\geq 90\%$ or to < 200 mg per 24h. If the serum and urine M-protein are unmeasurable, a $\geq 50\%$ decrease in the difference between involved and uninvolved FLC levels is required in place of the M-protein criteria

- **Stable Disease (SD)**

Not meeting criteria for CR, VGPR, PR or progressive disease. All categories also require no known evidence of progressive or new bone lesions if radiographic studies

were performed. Radiographic studies are not required to satisfy these response requirements.

- **Progressive disease (PD)**

Requires any one or more of the following:

Increase of $\geq 25\%$ from lowest response value in the following on 2 consecutive measurements:

- Serum M-component and/or (the absolute increase must be ≥ 0.5 g/dl). The serum M-component increases of ≥ 1 gm/dl are sufficient to define relapse if starting M-component is ≥ 5 g/dl.
- Urine M-component and/or (the absolute increase must be ≥ 200 mg/24h
- Only in patients without measurable serum and urine M-protein levels: the difference between involved and uninvolved FLC levels. The absolute increase must be >10 mg/dl.
- Bone marrow plasma cell percentage: the absolute % must be $\geq 10\%$
- Definite development of new bone lesions or soft tissue plasmacytomas or definite increase in size of existing bone lesions or soft tissue plasmacytomas

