- For aspirate specified for flow cytometry under the direction of [name], immediately discharge 1 mL of aspirated marrow syringe into a 10mL sodium heparin Vacutainer, cap tube tightly and mix by gentle inversion 5-6 times. Label tube with patient name, unique identifier number and date. Deliver immediately to the Flow Cytometry Laboratory B1B58 (specimens containing hematopoietic neoplasms have a tendency to clot and must be processed immediately). Call for STAT Escort pickup and delivery if you cannot deliver the specimen yourself [contact]). Aspirate from marrows at baseline, end of cycle 8/or CR reached between cycles 1-8, end of cycle 20/or CR reached between cycles 9-20 and during treatment termination/or CR reached between cycles 21 and beyond will be sent for plasma cell flow cytometry immunophenotyping at [name]'s lab.
- For aspirate specified for flow cytometry under the direction of [name], immediately discharge 1 mL of aspirated marrow syringe into heparin syringe tube.
- For aspirate designated for CD138 sorting, VDJ sequencing, exome sequencing, and microenvironment studies, send remaining aspirate sample [name] Laboratory in the Department of Laboratory Medicine Clinical Center (Attn: [name], [name]). Place aspirate sample in EDTA syringe immediately on ice. Transfer within 30 minutes of sampling to the lab for processing. CD138+ plasma cells will be viably frozen and batched to be sent to Adaptive Technologies for VDJ

Abbreviated Title: CRd in Newly Diagnosed MM
Version Date: 03/27/2020

sequencing and to MSKCC for exome sequencing. CD138- fractions will be studied by Dr.'s [name] and [name]. At subsequent time points, CD138+ sorting will not be done if the patient is in remission.

- For aspirate specified for cytogenetics/FISH, aspirate will be sent to [name]. (NOTE: [name] no longer at NIH/NCI, her involvement ended and these studies no longer being done as of Amendment M.)

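### Calendar footnote o ties the cycle 21–32 marrow to CR not being achieved, against its own column heading, the Section 5.1 table and Appendix B, so a late CR may be dated late

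*Combined protocol and SAP*

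**What the plan says.** Section 3.4, footnote o, sets the marrow schedule phase by phase. In cycles 1–8 and again in cycles 9–20 the marrow is due when CR is reached, or at the end of cycle 8 or cycle 20 if it is not. For cycles 21–32 the footnote asks for it "during cycles 21-32 (extended dosing phase II) if CR is not achieved or at treatment termination".

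Other places set the same time point differently:

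- The calendar column that carries footnote o is headed "Phase II-CR achieved (Cycle 21-32)/ Treatment termination".
- The correlative sampling table in Section 5.1 has "if CR achieved during cycles 21- 32/End of Cycle 32/treatment termination".
- Appendix B (Section 15.2) says aspirate taken "during treatment termination/or CR reached between cycles 21 and beyond will be sent for plasma cell flow cytometry immunophenotyping".
- Footnote n gives the paired PET rule as "during cycles 21-32 (extended dosing phase II) if CR is achieved or at treatment termination". Sections 3.3.7.7 and 5.1.4.1.1 agree with it.

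Section 6.3.3.1 defines CR as "Negative immunofixation on the serum and urine and disappearance of any soft tissue plasmacytomas", and the same sentence goes on to require no more than 5% plasma cells in the marrow. sCR adds a normal free light chain ratio and absence of clonal cells in the marrow.

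**The concern.** Footnote o is an operative schedule rule, and for one phase of treatment it reverses the condition used everywhere else. The marrow is the one part of the CR definition that cannot be read from blood, urine or imaging, so its date can fix the date on which CR is met. Section 6.3.4 starts the duration of response when the criteria for best response are met, so a late marrow can move that start. Section 1.1.2 makes MRD by flow cytometry and PET/CT, in relation to outcome, a secondary objective. If the PET is triggered at CR and the marrow is not, the two MRD measurements separate in this phase only.

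The rule is also incomplete as written. In the two earlier phases the marrow for a patient without CR has a named cycle (8 or 20). In cycles 21–32 it has none apart from treatment termination. Staff cannot tell when the procedure is due, or whether omitting it is non-adherence to be logged under Section 8.8.

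**Working it through.** The plan states no figure on this point, so the check is a comparison of text and one bound on delay.

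**Step 1: the trigger for cycles 21–32, place by place.**

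- Footnote o (marrow): CR not achieved, or treatment termination.
- Calendar column heading that carries footnote o: CR achieved, or treatment termination.
- Section 5.1 table (marrow correlates): CR achieved, or end of cycle 32 or termination.
- Appendix B (aspirate for flow cytometry): CR reached, or termination.
- Footnote n and Sections 3.3.7.7 and 5.1.4.1.1 (PET): CR achieved, or termination.

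Footnote o stands alone. It also differs from its own rule for the two earlier phases.

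**Step 2: who is affected under a literal reading.** Start with patients who first meet the blood and urine criteria for CR in cycles 21–32. Remove those already MRD negative on extended dosing: footnote o reads their protein clearance as CR without a repeat marrow, and Section 5.1.1(a) makes extension-phase marrows optional for patients MRD negative at the end of cycle 8. Those left still need a marrow for CR, and footnote o gives them none at protein clearance. The next scheduled one is at treatment termination.

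**Step 3: how long they could wait.** Phase II runs from cycle 21 through cycle 32 (Section 3.2.6), so it has 32 − 20 = 12 cycles of 28 days. Section 6.3.1 assesses response at cycles 21, 24, 27 and 30 and at the end of cycle 32. If treatment runs to the end of cycle 32 without delay, the wait from first clearance is:

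- day 1 of cycle 21: 12 × 28 = 336 days (48 weeks)
- day 1 of cycle 24: 9 × 28 = 252 days
- day 1 of cycle 27: 6 × 28 = 168 days
- day 1 of cycle 30: 3 × 28 = 84 days

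The 336 days is an upper bound. A patient without CR is due a marrow at the end of cycle 20, so one who clears protein on day 1 of cycle 21 may already have a recent result. Earlier termination, or a marrow ordered by the investigator, shortens any of these waits.

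**Step 4: which analyses can move.** The duration of response starts at best response, so for an affected patient it could be shortened by as much as the wait in step 3. The primary endpoint is scored in the first two completed cycles (Section 10.2). ORR is taken after 8 cycles (Section 6.3.7). PFS and OS run from the start of treatment (Sections 6.3.5 and 6.3.6) and do not use the CR date.

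**The case against.** The strongest reply is that this is a wording slip that the rest of the plan overrides. Staff working from the calendar see the CR trigger in the column heading, and the sampling table and Appendix B repeat it. The investigator may repeat a marrow under footnote o, and research marrows have been at the investigator's discretion since Amendment L. All of this stands, and it makes harm in practice less likely. It does not settle which instruction governs, and Amendment L did not change the CR definition.

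A sharper reply is that a patient with protein clearance but no marrow has not yet achieved CR as defined, so footnote o still covers that patient. The reading is possible. It would also bring in every other patient without CR, at no stated cycle, which the other places do not do. It shows that the footnote is ambiguous; it does not remove the conflict.

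Two stronger readings are tempting, and the documents do not support them. A reader might infer that new CRs in phase II never get the marrow that their definition requires. They do not lose it: footnote o keeps the termination marrow, waives a repeat for MRD-negative patients and allows one at discretion. A reader might also infer that biopsies are being directed at patients for whom no criterion needs them. Marrows in patients without CR are already planned at the end of cycles 8 and 20, the Section 5.1 table includes the end of cycle 32, and marrow plasma-cell percentage is one of the progression criteria in Section 6.3.3.1.

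**Conclusion.** The contradiction is real and sits in current, operative text. Its consequence is modest: for a patient not already MRD negative who first clears protein in cycles 21–32, CR or sCR may be dated up to about 336 days late, and the marrow MRD sample is not taken with the PET at CR. This assumes that footnote o is followed literally, that treatment continues to cycle 32 without delay, and that no discretionary marrow is done.

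The effect is limited to late CR dating, duration of response and phase II MRD samples. A reported CR rate would be touched only if best response were counted beyond cycle 8; the secondary objective places it after 8 cycles. The primary toxicity endpoint, the sample size, ORR after 8 cycles, PFS and OS are unaffected.

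The documents do not say how many patients are concerned. The number is likely small: the target is 45 evaluable patients, phase II is optional, and Section 1.2.10 reports 15/20 (75%) at nCR/sCR after a median of 7 cycles. That last figure includes nCR, which does not require negative immunofixation, so it supports only a rough judgement. This is a minor correction.

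**What to change.** Reconcile footnote o with its column heading, the Section 5.1 table and Appendix B, so that one marrow trigger governs cycles 21–32, and check that it fits the marrow requirement in the CR definition and the paired PET rule. If a marrow without CR is intended in this phase, name the cycle in which it falls due. Which trigger applies is for the investigators to decide; the need is that all these places say the same.

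Section 13.1.1 describes active recruitment and treatment in the past tense, so these visits may already be complete. In that case, state which trigger was applied when late CR dates, duration of response and phase II MRD results are reported, and give the number of patients whose first protein clearance fell in cycles 21–32.

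The cost is an edit to one footnote and a sentence in the report. If footnote o is aligned with the other places, no procedure is added beyond what they already call for.

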3.3.7 Monitoring

- 3.3.7.1 Patients will be observed in the hospital for administration of cycle 1 Days 1 and 2 of therapy.
- 3.3.7.2 Routine labs (cbc, chemistry panel 14, LDH, magnesium, uric acid, phosphate) will be performed on Day 1, 2, 8, 15, and 22 of cycle 1 and Day 1 (or within 2 days prior to day 1) of each cycle during cycles 1-8 and on Day 1 (or within 7 days prior to day 1) of every third cycle during extension phases I and II.
- 3.3.7.3 Myeloma tests include serum protein electrophoresis, serum immunofixation, serum free light chains, quantitative immunoglobulins, beta-2 microglobulin and will be performed at baseline and Day 1 (or within 2 days prior to day 1) of each cycle in the induction phase and on Day 1 (or within 7 days prior to day 1) of every third cycle during extension phase I and II. Subsequent serum immunofixation will only be performed on those patients clinically indicated.
- 3.3.7.4 Random urine sample for protein electrophoresis (UPEP) and immunofixation to assess for monoclonal protein in the urine (Bence-Jones proteinuria) to be performed at baseline, day 1 (or within 2 days prior to day 1) of each cycle during cycles 1-8, and day 1 (or within 7 days prior to day 1) of every third cycle during extension phase I and II. If patient obtains CR, then a 24 hour UPEP will be performed to confirm CR status. In patients whose measurable disease is best determined by measuring Bence-Jones protein quantification, a 24-hr UPEP will be performed at baseline, day 1 of each cycle 1-8, and day 1 of every third cycle during extension phase I and II. Otherwise, 24-hr UPEP Bence-Jones quantification will be estimated from random UPEP specimens performed at baseline, day 1 of each cycle 1-8, and day 1 of every third cycle during extension phase.
- 3.3.7.5 Patients will have clinic visits with H&P or standard progress notes assessing for toxicity/side effects on Day 1, 2, 8, 15, and 22 of cycle 1 and Day 1 of each cycle during cycles 1-8 and on Day 1 of every third cycle during extension phases I and II.

(This can be delayed up to one week per PI discretion for clinical and/or logistical reasons).

- 3.3.7.6 Additional laboratory studies and clinic visits will be performed if clinically indicated.

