- Development of hypercalcemia that can be attributed solely to the plasma cell proliferative disorder

- **Relapse from CR**

Any one or more of the following:

- Reappearance of serum or urine M-protein by immunofixation or electrophoresis. (Appearance of monoclonal or oligoclonal bands that are different from original isotype may not be defined as “relapse from CR”. Oftentimes, such bands may indicate fluctuations in immunological parameters that are not reflective of MM disease. In these situations, immunofixation and electrophoresis will be interpreted by the clinician before being labeled as “relapse”. ([32](#), [33](#)))
- Development of $\geq 5\%$ plasma cells in the bone marrow
- Appearance of any other sign of progression (i.e., new plasmacytoma, lytic bone lesion, hypercalcemia)

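### Calendar footnote o lets MRD-negative patients on extended lenalidomide be called CR on looser terms than the CR definition in 6.3.3.1

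*Combined protocol and SAP*

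**What the plan says.** Section 6.3.3.1 defines CR as "Negative immunofixation on the serum and urine and disappearance of any soft tissue plasmacytomas", together with at most 5% plasma cells in the marrow. It defines nCR as "Defined as absence of myeloma protein on electrophoresis, independent of immunofixation status". One route to VGPR is "Serum and urine M-protein detectable by immunofixation but not on electrophoresis".

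Footnote o of the study calendar (section 3.4) deals mainly with marrow timing, but it also contains a scoring rule. The rule begins "For patients who are on extended dosing with lenalidomide and are found to be negative by immunohistochemistry and flow cytometry" of the bone marrow, a state the footnote equates with MRD negativity. For these patients, "clearance of abnormal protein in blood and/or urine does not mandate a repeated bone marrow and the results will be interpreted as complete response". The investigator may still repeat the marrow.

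On the assays, section 3.3.7.3 begins "Myeloma tests include serum protein electrophoresis, serum immunofixation, serum free light chains, quantitative immunoglobulins, beta-2 microglobulin and will be performed at baseline and Day 1" of each induction cycle, and then of every third extension cycle. It ends: "Subsequent serum immunofixation will only be performed on those patients clinically indicated". No trigger is given. Section 3.3.7.4 and footnote m keep urine electrophoresis and immunofixation on schedule and add a 24-hour urine electrophoresis to confirm CR.

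Section 10.3.1 commits to reporting the CR rate and the VGPR+CR rate with 95% confidence intervals and gives no time point. Section 6.3.4 starts response duration on the date the best-response criteria are met.

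**The concern.** Waiving a repeat marrow in a patient already negative by immunohistochemistry and flow is reasonable. The footnote goes further: it says the result counts as CR, on a condition weaker than the definition in every respect except the marrow. Someone scoring responses from the calendar and someone scoring from 6.3.3.1 can give different labels to the same patient.

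The looser rule is available only to MRD-negative patients. Where it is used, the CR rate can rise, the start of response can be dated to an event the definition would not recognise, and CR and MRD negativity will agree partly by construction. MRD in relation to outcome is a secondary objective (1.1.2), and section 12.4 presents MRD as something to be set against the standard response criteria.

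**Working it through.** The plan gives no figure on this point. Its calculated design figures (10.2, 10.3.1) concern grade 3+ neurologic toxicity and do not use CR. They reproduce: the probability of 5 or more events in 45 is 7.3% at a true rate of 5% and 82.5% at 15%, and the exact 90% interval for 5/45 is 4.5% to 22.0%. The check here is therefore a comparison of rules.

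**Step 1. The two rules, limb by limb**

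| Limb | 6.3.3.1 | Footnote o |
|---|---|---|
| Serum | immunofixation negative | cleared, assay unstated; not needed if urine clears |
| Urine | immunofixation negative | cleared, assay unstated; not needed if blood clears |
| Plasmacytoma | gone | not mentioned |
| Marrow | at most 5% plasma cells | earlier sample negative by immunohistochemistry and flow |

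**Step 2. Patients whose label differs (all on extended dosing)**

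- MRD negative, electrophoresis clear in serum and urine, serum immunofixation still positive. Footnote o, read literally: CR. 6.3.3.1: nCR or VGPR.
- MRD negative, serum clear, urine still immunofixation-positive. Footnote o: CR on blood alone. 6.3.3.1: not CR; the category depends on the urine electrophoresis and amount.
- MRD negative, protein clear, plasmacytoma still present. Footnote o: CR. 6.3.3.1: not CR. PET is optional during extension for patients MRD negative at the end of cycle 8 (3.3.7.7), so this limb may go unimaged by PET in the group concerned.
- MRD positive, with the protein results of the first case. Both rules: nCR or VGPR. The first and fourth patients differ only in MRD status, yet one is CR and the other is not.

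**Step 3. Which results can move**

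- *CR rate.* With 45 evaluable patients (10.2), one relabelled patient adds 1/45 = 2.2 points. As an illustration only, assume 20/45 CRs under 6.3.3.1, with exact 95% intervals: 44.4% (29.6 to 60.0). One extra gives 46.7% (31.7 to 62.1), three give 51.1% (35.8 to 66.3), five give 55.6% (40.0 to 70.4). Both the base of 20 and the number of extras are assumptions.
- *VGPR+CR rate.* It is unchanged if the patient would otherwise be VGPR and rises if the patient would be below VGPR. For nCR it is undetermined, because 10.3.1 does not say whether nCR counts.
- *Duration of response.* A patient whose best response was a VGPR reached earlier gets a later start date once relabelled CR.
- *ORR after 8 cycles (6.3.7).* No effect: the footnote operates only from cycle 9.
- *Primary endpoint and sample size.* No effect.

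**Step 4. Serum immunofixation**

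CR under 6.3.3.1 cannot be established without it, and nCR ignores it. If the last sentence of 3.3.7.3 restricts the test during treatment, an electrophoresis-negative patient without the test cannot be placed in CR rather than nCR. Relapse from CR includes "Reappearance of serum or urine M-protein by immunofixation or electrophoresis", so a relapse visible only on serum immunofixation could be dated late.

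**The case against.** The strongest reply is that footnote o belongs to the bone marrow row, is about whether to repeat a marrow, and leaves response to 6.3.3. Entry was allowed on serum, urine or light-chain disease, so the and/or may mean whichever compartment held the protein. This is a fair guess at intent, but the footnote does not say it. It does say how the result will be scored, and the kinder reading still leaves the assay and plasmacytoma conditions open.

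There are also partial safeguards. Urine immunofixation stays scheduled, a 24-hour urine electrophoresis confirms CR, and 6.3.2 requires two consecutive determinations. They lower the risk on the urine side. None requires negative serum immunofixation, and repeating a determination does not change which assay or compartment counts.

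On 3.3.7.3 the reply largely succeeds. A reader might infer that the section schedules serum immunofixation and then takes it away. The last sentence can equally mean testing after the listed visits, and a suspected CR could itself be an indication. Calendar footnote f, attached to the myeloma tests row, was not in the text available for this review and may settle it. The most that can be said is that the two sentences are ambiguous.

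A reader might also infer that relapse from CR is found only when someone decides to test. The documents do not support this. Serum electrophoresis and urine immunofixation remain scheduled, and relapse can also be declared on electrophoresis, marrow, a new plasmacytoma, a lytic lesion or hypercalcemia. Only a relapse confined to serum immunofixation is exposed. Extension assessments are 3 x 28 = 84 days apart, but a missed test does not generally cost that interval: the delay is zero if any other criterion is met at the visit.

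**Conclusion.** The point stands for footnote o. Followed literally, it labels as CR some patients whom 6.3.3.1 places in nCR, VGPR or lower, and it does so only for MRD-negative patients. It can raise the reported CR rate by 2.2 points per patient, move the start of response duration, and build in part of any CR-MRD association. The 3.3.7.3 point is secondary: an ambiguity whose effect depends on how it was applied.

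The total size is unknown. A reader might try to derive it from the interim results in 1.2.10, where 5 of 20 patients were below nCR/sCR (5/20 x 45, about 11 of 45). That does not work. It leaves out nCR patients, who are obvious candidates for relabelling because nCR ignores immunofixation, and the documents do not say how many patients are MRD negative with incomplete clearance. No range of percentage points can be drawn from it.

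The conclusion assumes that the footnote is applied as written and that extension-phase responses count toward the rates in 10.3.1, which sets no time point.

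**What to change.** - **Footnote o:** state that the earlier MRD-negative marrow stands in for the marrow limb only, and that CR otherwise follows 6.3.3.1: immunofixation negative in serum and in urine, and no soft tissue plasmacytoma.
- **Section 3.3.7.3:** reconcile its two sentences, and calendar footnote f if needed, so that serum immunofixation is run on the scheduled sample whenever electrophoresis shows no M-protein.
- **Analysis:** re-score by 6.3.3.1 every CR assigned under footnote o, and list those with no serum immunofixation result. Section 13.1.1 describes recruitment and carfilzomib treatment in the past tense, so this step matters most for the reported results.

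The cost is two reworded passages, a review of the affected records, and a few added assays on serum already drawn. The CR rate may come out slightly lower.
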